For Part 2 MAD Cohorts 3, 4 and 5, 24-hour continuous Holter/ECG recordings will be collected, on the day before the first dose (Day -1), Day 1, and Day 14 for extraction of ECGs paired with PK sampling. In addition, 12-Lead ECGs will be collected for Part 2 at timepoints indicated in the SoA.

Participants in Part 2 will have a screening visit within 28 days prior to first dose and a follow-up visit approximately 28 days after the last dose. Flexibility of visit scheduling may be required if a pandemic situation applies (see [Appendix 7](#)). Otherwise, study assessments will be performed as indicated in [SoA](#). Study participants will be confined to the clinic from Day -2 until discharge with requirement to complete all scheduled outpatient visits. Maximum duration of study participation from admission into the unit until completion of follow visit will be approximately 5 weeks.

Part 3 (RBA):

Part 3 is a randomized, open-label, single-dose, 3-period crossover optional Cohort 7 to compare the RBA of the GSK3739937 PiB with GSK3739937 Tablet and to assess the effect of food on the safety, tolerability and PK of GSK3739937 Tablet in healthy participants. In Part 3, approximately 18 participants will be treated to ensure that 12 evaluable participants complete Cohort 7. If participants prematurely discontinue Part 3, additional participants may be randomized after consultation with the sponsor to ensure that 12 evaluable participants complete the study.

Part 3 will consist of a screening period and 3 sequential treatment periods with a single dose of study intervention per treatment period.

Prior to dosing on Day 1 of Period 1, participants will be randomly assigned to 1 of 3 treatment sequences (ABC, BAC or CAB). Participants will receive each of the following treatments administered as 1 treatment per period:

- Treatment A: GSK3739937 PiB, 100 mg (administered as oral suspension) administered under moderate fat conditions (reference)
- Treatment B: GSK3739937 Tablet, 100 mg (single dose given as a 100 mg tablet(s)) administered under moderate fat conditions (test)
- Treatment C: GSK3739937 Tablet, 100 mg (single dose given as 100 mg tablet(s)) administered under fasted conditions (reference).

To ensure adequate washout, there will be at least 24 days between each dose of study intervention, with an allowance window of 4 hours (i.e., 24 days minus 4 hours) to allow flexibility in scheduling participants for dosing at the clinic.

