assessments will be performed as indicated in [SoA](#). Study participants will be confined to the clinic from Day -2 until discharge with requirement to complete all scheduled outpatient visits. Maximum duration of study participation from admission into the unit until completion of follow visit will be approximately 5 weeks.

Part 2 MAD: Dose Escalation

Dose escalation in Part 2 will be determined by the VH/GSK study team and the PI based on the double-blind (sponsor-unblinded) safety and PK data (minimally up to 15 days following the last dose) from the previous dosing Cohort (s). Specifically, safety and PK data through Day 29 in Cohorts 3 and 4 and through Day 33 in Cohort 5 from a minimum of five participants receiving active drug will be required for dose escalation.

Part 3 (RBA FE)

Part 3 will involve a randomized, open-label, single-dose, 3-period crossover optional Cohort 7 to compare the RBA of the GSK3739937 PiB with GSK3739937 Tablet and to assess the effect of food on the safety, tolerability and PK of GSK3739937 Tablet in healthy participants. In Part 3, approximately 18 participants will be treated to ensure that approximately 12 evaluable participants complete Cohort 7. If participants prematurely discontinue Part 3, additional participants may be randomized after consultation with the sponsor to ensure that approximately 12 evaluable participants complete the study.

[figure not shown]
Part 3 will consist of a screening period and 3 sequential treatment periods with a single dose of study intervention per treatment period.

Prior to dosing on Day 1 of Period 1, participants will be randomly assigned to 1 of 3 treatment sequences (ABC, BAC, or CAB). Participants will receive each of the following treatments administered as 1 treatment per period:

- Treatment A: GSK3739937 PiB, 100 mg (administered as oral suspension) administered under moderate fat conditions (reference)
- Treatment B: GSK3739937 Tablet, 100 mg (single dose given as 100 mg tablet(s)) administered under moderate fat conditions (test)
- Treatment C: GSK3739937 Tablet, 100 mg (single dose given as 100 mg tablet(s)) administered under fasted conditions (reference).

To ensure adequate washout, there will be at least 24 days between each dose of study intervention, with an allowance window of 4 hours (i.e., 24 days minus 4 hours) to allow flexibility in scheduling participants for dosing at the clinic.

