9.4.4. Statistical Analysis of Pharmacokinetic Data

- Statistical analyses of the pharmacokinetic parameter data will be the responsibility of Clinical Statistics, GSK.
- Plasma VH3739937 concentrations and PK data will be summarized by treatment and listed by participant. Unless stated otherwise, descriptive summaries will include number (n), mean, standard deviation (SD), coefficient of variation (%CV), median, minimum, and maximum for continuous variables, n and percent (%) for categorical variables, and geometric mean, 95% confidence interval (CI), and the between-participant CV (%CVb) for the log-transformed PK parameters.
- Dose proportionality of selected single and repeated dose PK parameters will be assessed by the power model.

- Accumulation will also be:
 - Predicting from single dose data (Part 1) based on AUC as follows: $R_p = \frac{AUC(0-\infty)}{AUC(0-\tau)}$ day 1 / $AUC(0-\tau)$ day 1
 - Evaluated for each treatment by determining the ratio of Day 14 for cohort 3 and 4, Day 18 for cohort 5, and Day 15 for cohort 6 (Part 2) to Day 1 $AUC(0-\tau)$ ($R(AUC(0-\tau))$), C_{max} ($R(C_{max})$), and C_{τ} ($R(C_{\tau})$). C_{24} on Day 1 will be taken as the C_{τ} on that day.
- Assessment of steady-state VH3739937 concentrations will be assessed in Part 2 by estimating the slope of pre-dose concentrations on Days 2-14 for Cohorts 3 and 4, Days 2-18 for Cohort 5 and Days 2-15 for Cohort 6. The final assessment of the slope will be determined by at least the last 3 pre-dose concentrations.
- **Part 3**
For the assessment of relative bioavailability of formulation and food effect (if conducted), the \log_e -transformed PK parameters will be analysed as data permits using separate mixed effect models with a fixed effect term for fed vs. fasted and tablet vs PiB. Participant will be treated as a random effect in each model. Point estimates and their associated 90% CIs will be calculated for the difference in $AUC_{(0-24)}$, $AUC_{(0-\infty)}$, and C_{max} for the tablet vs PiB and fed vs fasted comparisons. The point estimates and their associated 90% CIs will then be back-transformed to provide point estimates and 90% CIs for the ratios of tablet vs PiB and fed vs fasted in PK parameter values on the original scale.
- Full details of the statistical analysis of PK data will be described in the RAP.

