	
Part 3 (RBA/FE):
 
 • In Part 3 participants will randomly be assigned to receive a random sequence of the following treatments: 
 ○ Treatment A: VH3739937 PiB, 100 mg (administered as oral suspension under moderate fat conditions (reference)) ○ Treatment B: VH3739937 Tablet, 100 mg (single dose given as a 100 mg tablet(s)) administered under moderate fat conditions (test) ○ Treatment C: VH3739937 Tablet, 100 mg (single dose given as 100 mg tablet(s)) administered under fasted conditions (reference) • In Part 3, participants will be assigned to one of three sequences according to a Latin square design. The three sequences are: 
 ○ A/B/C ○ B/C/A ○ C/A/B
Interim Analysis	
 • All preliminary safety, tolerability, and available PK data will be reviewed internally at ViiV/GSK prior to each dose escalation. Safety data (labs, vital signs, ECG, AEs, SAEs) will be reviewed by the PI/Sub-I and ViiV/GSK study team after completion of each dose level. • Dose escalation can only occur after DEC has found that the safety and PK profiles are supportive to proceed with the evaluation of the next higher dose level (See Protocol Section 4.3.6 Dose Escalation Committee).

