2.4.2. Part 3 (RBA)

The purpose of Part 3 is to evaluate the relative bioavailability and food effect of two differing formulations of VH3739937 (tablet vs. powder in a bottle). For the assessment of relative bioavailability of formulation and food effect the log-transformed PK parameters will be analysed as data permits using separate mixed effect models with fixed effect terms for fed vs. fasted and tablet vs PiB. Participant will be treated as a random effect in each model. Point estimates and their associated 90% CIs will be calculated for the difference in $AUC_{(0-24)}$, $AUC_{(0-\infty)}$, and C_{max} for the tablet vs PiB and fed vs fasted comparisons. The point estimates and their associated 90% CIs will then be back-transformed to provide point estimates and 90% CIs for the ratios of tablet vs PiB and fed vs fasted in PK parameter values on the original scale.

No formal statistical hypothesis will be tested. The mixed model will be used to estimate relative bioavailability and food effect but will not be used to justify statistical bioequivalence.

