8.1.5.1.4. Relative Bioavailability and Food Effect

Part 3

The following pharmacokinetic statistical analyses will only be performed if sufficient data is available (i.e. if participants have well defined plasma profiles).

Endpoint / Variables

 • Log-transformed $AUC(0-24)$, $AUC(0-\infty)$ (or $AUC(0-t_{last})$ if $AUC(0-\infty)$ cannot be derived), and C_{max}
Model Specification

 • $AUC(0-24)$, $AUC(0-\infty)$ and C_{max} will be separately analysed using a mixed effects models. In each model the dependent variable will be the log-transformed PK parameter of interest ($AUC(0-\infty)$ or C_{max}). • For the RBA model the primary comparison will be Tablet vs. PiB (B vs. A), the independent variables will include a fixed effect for treatment (PiB or Tablet) and period, and a random effect for participant. • For the Food effect model the primary comparison will be Tablet Fed vs. Tablet Fasted (B vs. C), the independent variables will include a fixed effect for fasting status (fed vs. fasted) and period, and a random effect for participant $\log(Pk\ Parameter) = \beta_0 + \beta_1 Treatment + \beta_2 Period + \gamma_i Subject$

Model Checking & Diagnostics

 • A compound symmetry covariance structure for the R matrix will be used by specifying “type=CS” on the RANDOM line • In the event that this model fails to converge, alternative correlation structures may be considered such as CSH. • The Kenward and Roger method for approximating the denominator degrees of freedom and correcting for bias in the estimated variance-covariance of the fixed effects will be used. • Normality assumptions underlying the model used for analysis will be examined by obtaining a normal probability plot of the residuals and a plot of the residuals versus the fitted values (i.e. checking the normality assumption and constant variance assumption of the model respectively) to gain confidence that the model assumptions are reasonable. • If there are any departures from the distributional assumptions, alternative models will be explored using appropriate transformed data.
Model Results Presentation

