
 • The estimated difference and CI obtained on the log scale will be exponentiated to provide an estimate of the fed to fasted or tablet to PiB ratio and its associated 90% CI. Estimates of within-subject variability (%CVw) will also be provided (%CVw=SQRT(exp(MSE) – 1)×100). %CVw represents a pooled measure of within-subject variability across all treatments. • Comparative plots of individual PK parameters will be generated by treatment on linear and semi-logarithmic scales. • Plots of adjusted geometric mean ratio of test to reference treatment together with 90% confidence intervals will be produced. • Listing of individual PK parameter ratios will be generated. • Supportive SAS output from statistical analysis will be generated.
Subgroup Analyses

 • Not Applicable.
Sensitivity and Supportive Analyses

 • Not Applicable.

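### Part 3: the protocol and the SAP randomise to different sequence sets, and the protocol's precision tables fit only a period-balanced set; the SAP also does not say which treatments' data enter each model

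*Protocol*

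**What the plan says.** **Sequences.** The synopsis (protocol 1.1) states that "participants will be randomly assigned to 1 of 3 treatment sequences (ABC, BAC or CAB"), and protocol 4.1 repeats the list: "participants will be randomly assigned to 1 of 3 treatment sequences (ABC, BAC, or CAB"). SAP 2.3 says that "participants will be assigned to one of three sequences according to a Latin square design" and lists A/B/C, B/C/A and C/A/B. The second sequence is therefore BAC in one document and BCA in the other.

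**Model.** Protocol 9.4.4 plans "separate mixed effect models with a fixed effect term for fed vs. fasted and tablet vs PiB", with participant random and no period term, and leaves full details to the reporting and analysis plan. SAP 2.4.2 says nearly the same ("separate mixed effect models with fixed effect terms for fed vs. fasted and tablet vs PiB") and also names no period. SAP 8.1.5.1.4 does include it. For relative bioavailability, "the independent variables will include a fixed effect for treatment (PiB or Tablet) and period, and a random effect for participant"; the food-effect model is built the same way with fasting status as the factor, and the equation repeats period. The contrasts are fixed: B vs A for formulation and, in the SAP's words, "For the Food effect model the primary comparison will be Tablet Fed vs. Tablet Fasted (B vs. C"). No section says whether C data enter the first model or A data enter the second.

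**Precision.** Protocol 9.2.1 states a log half-width of 0.173 and a 90% interval of (0.841, 1.189) for 12 participants, CVw 25% and ratio 1.0. Tables 13 and 14 extend this to other n, CVw and ratios.

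**The concern.** Two different sequence sets cannot both govern one randomisation list. The choice has consequences because the B/A and B/C ratios of AUC(0-24), AUC(0-inf) and Cmax are primary endpoints of Part 3, and only one of the two sets spreads each treatment evenly over the three periods. On an unbalanced set, adjusting for period costs precision. The interval given as the expected precision would then not be the one the design delivers.

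The data entering each model is a lesser question of the same kind. Using all three treatments or only the two compared changes the residual degrees of freedom, and so the interval.

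**Working it through.** **Inputs.** n = 12, 15, 18; CVw 15%, 25%, 35%; ratios 0.9, 1.0, 1.1 (protocol 9.2.1, 9.2.2). Sequence sets as quoted. Equal completers per sequence are assumed.

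**Formulae.** sigma_w = sqrt(ln(1 + CVw²)); half-width h = t(0.95, df) × sigma_w × sqrt(v); interval = ratio × exp(±h). For CVw 25%, sigma_w = sqrt(ln 1.0625) = 0.2462.

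**Step 1: reproduce the stated figure.** Take three treatments, period and participant on a period-balanced design. Then v = 2/n and df = 3n − n − 2 − 2 = 2n − 4. For n = 12: t(0.95, 20) = 1.725, so h = 1.725 × 0.2462 × 0.4082 = 0.173 and the interval is (0.841, 1.189), as stated. All 13 distinct intervals in Tables 13 and 14 match to three decimals. With df = 2n − 2 (no period) 6 of 13 match; with n − 1 or n − 2, none.

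**Step 2: period balance.** Number of sequences placing each treatment in periods 1/2/3:

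| Treatment | ABC, BAC, CAB | ABC, BCA, CAB |
|---|---|---|
| A | 1 / 2 / 0 | 1 / 1 / 1 |
| B | 1 / 1 / 1 | 1 / 1 / 1 |
| C | 1 / 0 / 2 | 1 / 1 / 1 |

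**Step 3: cost of the protocol set under the same model.** After adjustment for participant and period, the treatment information for (A, B, C) is (n/9) times the matrix with rows (4, −3, −1), (−3, 6, −3), (−1, −3, 4). Solving for B − A gives v = 2.4/n, and B − C is the same. Against 2/n the variance is 1.20 times as large and the half-width sqrt(1.20) = 1.095 times. For n = 12: h = 1.725 × 0.2462 × sqrt(0.2) = 0.190, interval (0.827, 1.209). For n = 15 (df 26): (0.845, 1.183) against the stated (0.858, 1.166). For n = 18 (df 32): (0.859, 1.165) against (0.870, 1.149).

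**Step 4: two-treatment models on the Latin square.** Each model then has 2n observations, so df = 2n − n − 2 − 1 = n − 3, and v stays 2/n. For n = 12: t(0.95, 9) = 1.833, h = 1.833 × 0.2462 × 0.4082 = 0.184, interval (0.832, 1.202). The ratio 0.184/0.173 is about 1.06.

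**The case against.** The strongest case against is that the model is largely settled. SAP 8.1.5.1.4 states period in both model descriptions and in the equation, and protocol 9.4.4 leaves full details to the SAP. That stands. A reader might infer that the period term is undefined, or that SAP 2.1 is wrong to report no change from the protocol, but a period term is the kind of detail that was deferred. What remains is the missing term in SAP 2.4.2 and the silence on the third treatment's data. The SAP's note that "CVw represents a pooled measure of within-subject variability across all treatments" does not settle this, since it may mean only the treatments in that model.

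Three stronger readings are tempting and are not supported:

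- **A loss of about 30%.** Protocol sequences with two-treatment, period-adjusted models give up to (0.798, 1.253). This takes the sequences from one document and a reading of the model from the other. It is also an upper bound, because a random participant effect recovers some information.
- **Biased ratios.** On the protocol sequences without a period term, log B/A would shift by one third of the period 3 minus period 2 difference, and log B/C by the opposite. This drops a term the SAP states and needs a period effect for which the documents give no figure. Carry-over hardly supplies one: with the stated half-life of about 90 h and a 24-day washout (576 h), about 0.5^(576/90) = 1.2% of a dose remains.
- **Fed and fasted tablets averaged against PiB.** A two-level tablet/PiB factor fitted to all data would do this, but SAP 5.1, 8.1.5.1.4 and 13.5.3 define the comparisons as B/A and B/C.

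It is also fair that the tables are indirect evidence of the intended model: protocol 9.2.1 names none, calls the interval approximate, and the match separates df 2n − 4 from 2n − 2 only by differences of 0.001. Any period-balanced three-treatment design would fit equally well. Finally, the ABC/BCA/CAB square has its own limit, since each treatment always follows the same predecessor.

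**Conclusion.** The sequence conflict is real: the protocol gives its list twice, so a single misprint does not explain it. The randomisation list and protocol Figures 2 and 4 are not available here, so which set governs cannot be told. If it is the protocol's set, the n = 12 interval is about 10% wider on the log scale than stated under the model the tables imply. The third-treatment question is minor, at about 6% if each model uses only its two treatments on the Latin square.

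These sizes rest on equal completers per sequence, which is not assured when about 18 are treated to obtain 12 evaluable. A 6/4/2 split on the Latin square with the three-treatment model already gives (0.834, 1.199). They also rest on a common within-participant variance.

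No hypothesis is tested (protocol 9.1), and SAP 2.4.2 rules out a bioequivalence claim. The point therefore concerns precision, period balance and agreement between documents, not a decision. It should be fixed.

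**What to change.** 1. Check the randomisation list and make protocol 1.1, protocol 4.1 and SAP 2.3 state one sequence set.
   - If Part 3 is not yet randomised, use ABC/BCA/CAB.
   - If ABC/BAC/CAB was used, correct SAP 2.3, drop the Latin square description, keep period in the model and replace the stated precision with the step 3 intervals for n = 12, 15 and 18 (three-treatment model).
2. Add period to SAP 2.4.2, and add one sentence to SAP 8.1.5.1.4 saying which treatments' data enter each model. Either choice is acceptable:
   - One model per PK parameter with a three-level treatment factor, period and random participant, and contrasts B − A and B − C. On the Latin square this supports Tables 13 and 14 as they stand. The downside is a common residual variance for fed and fasted treatments.
   - Separate two-treatment models, with the intervals restated. On the Latin square at ratio 1.0 and CVw 25%: n = 12 (0.832, 1.202), n = 15 (0.852, 1.174), n = 18 (0.866, 1.155). For n = 12: CVw 15% (0.894, 1.118), CVw 35% (0.775, 1.290).

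The cost is wording in two documents, one check of the list and possibly a restated table. No extra participants or procedures are needed.

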4.2. Scientific Rationale for Study Design

This is a first time in human study that will assess the safety, tolerability, and PK of VH3739937, an HIV-1 MI. The data gathered will inform subsequent clinical trials for VH3739937, including a Phase 2a POC study in HIV-1-infected participants as well as a FTiH study of VH3739937 administered parenterally (subcutaneously or intramuscularly).

All doses of VH3739937 in this study will be administered in the fed state with dosing occurring within 15 minutes of completing a standardized moderate fat meal, unless otherwise indicated in Part 3 Treatment C (i.e. within 5 minutes after completing the

meal). Data with previous MIs, GSK3532795 and GSK3640254, demonstrated that food was necessary to achieve dose proportional PK and target efficacious concentrations (see Section 2.2.1.). Given the structural similarities, including solubility limitations, between GSK3532795, GSK3640254 and VH3739937, administration of VH3739937 with food in this study is expected to enhance both bioavailability and the likelihood for linear PK, allowing for a rigorous assessment of safety and tolerability across a larger exposure range than would be allowed in the fasted state. Finally, VH intends to administer VH3739937 in the fed state in a future Phase 2a POC study in HIV-infected participants; the current study will assess the safety, tolerability, and PK of VH3739937 under the same conditions in healthy participants prior to dosing in HIV-infected participants. The relative bioavailability cohort is planned to assess the impact of the fasted and fed state on VH3739937 bioavailability.

In Part 2 of the study (MAD), doses up to 4 times the minimally anticipated effective dose following oral administration of the suspension formulation (25 mg) are planned to be evaluated in Cohorts 3 to 5 and a higher 500 mg weekly dose will be evaluated in Cohort 6. In future studies in HIV-1-infected participants, these doses/exposures may be evaluated to understand the relationship between VH3739937 exposures and efficacy, duration of response, and resistance development. Furthermore, assessment of this dose/exposure range (anticipated to be the therapeutic exposure range in the target population) in healthy participants will inform safety and tolerability prior to exposing a more vulnerable HIV-1-infected population to VH3739937 and will inform risk mitigation strategies for potential drug interactions.

This dose/exposure range in healthy participants is clinically reasonable based upon the preclinical profile of VH3739937 and the clinical profile of prior MIs (GSK3640254 and GSK3532795), and the planned inpatient and outpatient evaluation for potential treatment emergent risks: including QT prolongation, GI intolerance and neuropsychiatric safety – which will be frequently monitored in this limited dosing duration setting. The preliminary data observed to date in this study (212548) through 640 mg in the SAD and 25 mg QD for 14 days in the MAD have not highlighted a significant safety concern. Phase 1-2a studies with GSK3640254 have not evaluated for the presence of gastric toxicity in humans; thus, it is unclear if any of the GI AEs observed in any clinical trial were representative of, associated with, or resulted from gastric toxicity (if present). However, a currently active Phase 2b study of GSK3640254 includes a sub-study to assess the potential for GI toxicity.

